14.3 Statistical Analysis

14.3.1 Analysis Datasets

The following Analysis datasets are planned for this study:

Full Analysis Set (FAS): The FAS will include all eligible patients who receive at least one dose of protocol therapy. All efficacy endpoints will be analyzed using the FAS Population.

Safety Analysis Set: Safety analysis will be conducted using the Safety Analysis Set defined as any participant receiving one dose of study treatment.

14.3.2 Efficacy Analysis (arm 1 and 2)

Number and percent of patients who achieve overall response (CR or PR) by RECIST 1.1 will be summarized with 80% two-sided exact binomial confidence intervals (CI) in the FAS cohort. Subjects who have non-evaluable response, withdraw or die prior to the first response evaluation will be conservatively counted as non-responders in the primary analysis of ORR.

14.3.3 Determination of the MTD (arm 2)

Three to six patients will initially be treated for 28 days (1 cycle) and a safety evaluation will be done by the overall PI before any further patients are enrolled. MTD is defined as the highest dose studied at which no more than 1 of 6 subjects has experienced a DLT in cycle 1. If only three patients are treated at the MTD, an additional three patients will be added for a total of six patients at the MTD. The dose will be escalated either until an MTD is identified or the maximum planned dose is achieved.

14.3.4 Secondary Endpoints Analysis

Time to event endpoints (PFS, DOR and OS, as defined in section 12.1.4.5, 12.1.6 and 14.1.2) will be estimated using the method of Kaplan-Meier, for each treatment arm. Median and event-free rate at selected timepoints along with 95% confidence intervals will be provided.

For toxicity reporting, all adverse events will be graded and analyzed using CTCAE version 5. Type of adverse events, intensity (grading), and attribution will be provided in a listing. The worst grade will be used if any toxicity event is reported multiple times on the same participant. All adverse events resulting in discontinuation, dose modification, and/or dosing interruption, and/or treatment delay of drug will also be summarized. All laboratory test results will be classified according to the CTCAE version 5.

14.3.5 Quality of Life (QOL) Endpoints Analysis

The QOL will be measured by the Functional Assessment of Cancer Therapy-Kidney Symptom Index (FKSI)-19 and the Brief Fatigue Inventory (BFI). The questionnaires will be administered per schedule defined in section 11 (study calendar).

The FKSI-19 comprises of 19 items (each score ranging from 0-4) with a possible maximum total score of 76. The BFI is a 9 items questionnaire (each score ranging from 0-10) with a possible maximum score of 90. The calculated total scores at each timepoint and changes from baseline will be summarized with mean and standard deviation. Changes from baseline will be graphically presented. For FKSI-19, the proportion of patients with “clinically significant” symptoms (those scoring 3 or 4) will also be descriptively summarized over times across all items or by sub-domains. Missing assessments may be due to stopping treatment, not completing the FKSI or BFI assessments, and other reasons. Information on reasons why the patient did not complete the FKSI-19 or BFI Form will be collected.

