14.1.2 Secondary endpoints

Duration of response (DOR) as defined in section 12.1.4.5.

Progression-free survival (PFS) defined as the time from trial treatment start to the earlier of progression or death due to any cause. Participants alive without disease progression are censored at date of last disease evaluation.

Overall survival (OS) defined as the time from trial treatment start to death due to any cause, or censored at date last known alive.

Safety and tolerability according to NCI CTCAE v5.0.

Quality of life using FKSI-19 and BFI. The FKSI-19 is a 19 item questionnaire with each item scored on a scale of 0-4 for a total score of 0-76 with higher scores indicating fewer symptoms (Appendix D)²⁹. The BFI is a 9 item questionnaire with each item scored on a scale of 0-10. Scores are categorized as mild (1-3), moderate (4-6), or severe (7-10). A global fatigue score can be found by averaging the score obtained on each test item completed (Appendix E)³⁰.

Pharmacokinetics of abemaciclib and MK-6482.

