APPENDIX D FKSI-19

STUDY ID _____

STUDY NUMBER _____

DATE _____

Below is a list of statements that other people with your illness have said are important. **Please circle or mark one number per line to indicate your response as it applies to the past 7 days.**

		Not at all	A little bit	Some-what	Quite a bit	Very much
GP1	I have a lack of energy	0	1	2	3	4
GP4	I have pain	0	1	2	3	4
C2	I am losing weight	0	1	2	3	4
HI7	I feel fatigued	0	1	2	3	4
B1	I have been short of breath	0	1	2	3	4
BRM3	I am bothered by fevers (episodes of high body temperature)	0	1	2	3	4
BP1	I have bone pain	0	1	2	3	4
L2	I have been coughing	0	1	2	3	4
HI12	I feel weak all over	0	1	2	3	4
RCC 2	I have had blood in my urine	0	1	2	3	4
C6	I have a good appetite	0	1	2	3	4
GF5	I am sleeping well	0	1	2	3	4
GE6	I worry that my condition will get worse	0	1	2	3	4
GP2	I have nausea	0	1	2	3	4
C5	I have diarrhea (diarrhoea)	0	1	2	3	4
GP5	I am bothered by side effects of treatment	0	1	2	3	4
GF1	I am able to work (include work at home)	0	1	2	3	4

GF3	I am able to enjoy life	0	1	2	3	4
GF7	I am content with the quality of my life right now	0	1	2	3	4

DRS-P = Disease-related symptoms subscale – Physical

DRS-E = Disease-related symptoms subscale – Emotional

TSE = Treatment side effects subscale

FWB = Function and well-being subscale

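### The FKSI-19 rule that counts a 3 or 4 as a clinically significant symptom runs backwards for the five positively worded items

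*Combined protocol and SAP*

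**What the plan says.** Quality of life by FKSI-19 is a listed secondary endpoint in Section 14.1.2, which describes 19 items scored 0-4 "for a total score of 0-76 with higher scores indicating fewer symptoms". Section 14.3.5 repeats the range: "The FKSI-19 comprises of 19 items (each score ranging from 0-4) with a possible maximum total score of 76". It plans means, standard deviations and changes from baseline for the total, and then adds a proportion of patients with clinically significant "symptoms (those scoring 3 or 4) will also be descriptively summarized over times across all items or by sub-domains". Neither section describes reversal of any item, and 14.3.5 exempts none from the 3-or-4 rule.

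Appendix D prints the questionnaire. Every item uses the same five columns, from 0 (not at all) to 4 (very much). Five items describe a good state:

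- C6, "I have a good appetite"
- GF5, "I am sleeping well"
- GF1, "I am able to work (include work at home"
- GF3, "I am able to enjoy life"
- GF7, "I am content with the quality of my life right now"

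The other 14 describe symptoms, side effects or worry. Appendix D also names four subscales, one of which covers function and well-being.

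**The concern.** A symptom flag has to point the same way on every item it covers. Here a 3 or 4 means a bad state on 14 items and a good state on five. Any proportion that pools items, or that covers a sub-domain containing one of the five, would count wellness as a symptom and would miss loss of appetite, sleep, work or enjoyment.

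The change over time would also be misread. Section 7.1.1 lists decreased appetite in 46% of patients on single-agent abemaciclib, and C6 is the item that asks about appetite. A patient who falls from 4 to 0 on C6 would move from flagged to unflagged, so a worsening would be tabulated as an improvement.

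There is a second hazard. The total in 14.1.2 needs items oriented so that higher is better. A programmer who builds those item scores and reuses them for the 3-or-4 rule would invert the whole table.

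**Working it through.** **Inputs.** Item wording and response scale: Appendix D. Item range and maximum: 14.3.5. Direction of the total: 14.1.2. Planned numbers, 11 in arm 1 and 20 at the MTD in arm 2: 14.2.

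**1. Item count and the plan's maximum.**
- Negative: GP1, GP4, C2, HI7, B1, BRM3, BP1, L2, HI12, RCC2, GE6, GP2, C5, GP5 = 14.
- Positive: C6, GF5, GF1, GF3, GF7 = 5.
- 14 + 5 = 19, and 19 × 4 = 76, which reproduces the stated maximum.

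**2. What the direction in 14.1.2 requires.** Take a best-health patient (raw 0 on the negative items, 4 on the positive) and a worst-health patient (raw 4 and 0).
- Unreversed sums: best 14×0 + 5×4 = 20; worst 14×4 + 5×0 = 56. Higher would then mean worse.
- With the 14 negative items replaced by 4 − raw: best 14×4 + 5×4 = 76; worst 14×0 + 5×0 = 0. This agrees with 14.1.2.

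So the total requires reversal of the 14 negative items. The five positive items keep their raw value.

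**3. The 3-or-4 rule under each reading.**

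| Values used | Best health, items flagged | Worst health, items flagged |
|---|---|---|
| Raw answers | 5/19 = 26.3% | 14/19 = 73.7% |
| Oriented as in 14.1.2 | 19/19 | 0/19 |
| Only the five positive items reversed | 0/19 | 19/19 |

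Only the last row is correct, and neither section describes it. It is the opposite of the reversal needed for the total. Because the five positive items have the same value raw and oriented, they are wrong in both of the first two rows; the 14 negative items are wrong only in the second.

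**4. If the pooled summary means any item at 3 or 4, on raw answers.** The plan does not define the pooled summary, so this is one possible reading. With complete forms and every patient in best health, it would report 11/11 in arm 1 and 20/20 at the MTD. On the 14 negative items alone it would report 0/11 and 0/20. In general, the reported proportion could not fall below the proportion answering 3 or 4 on any positive item. With complete forms, each patient flagged only by a positive item adds 1/11 = 9.1 percentage points in arm 1, or 1/20 = 5.0 points at the MTD.

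**5. By sub-domain.** The available text does not show which items belong to which subscale. If every item belongs to one of the four, the five positive items must fall in at least one of them, so at least one sub-domain summary is affected.

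**The case against.** The best defence rests on the word symptoms. Sleeping well or enjoying life is not a symptom, so an analyst might limit the rule to the symptom items, or orient the others first. The plan already presupposes some reversal, since the total in 14.1.2 cannot work without it. On this view 14.3.5 lacks a detail and is not wrong. But the narrower reading conflicts with the stated scope, which takes in every item, and with a named function and well-being subscale among the sub-domains. The reversal that 14.1.2 presupposes does not help either: it makes the flag wrong on all 19 items.

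Several points on size do stand. The best- and worst-health patients are constructed to show direction; they do not represent refractory patients with ECOG status up to 2. The any-item definition is assumed. The 1/20 figure assumes an MTD-only denominator, although arm 2 enrols 23-26 patients and 14.3.5 does not restrict quality of life to the MTD. Both per-patient figures assume complete forms, and the plan expects some to be missing. The summary is supplementary and untested, and Sections 1.2 to 1.4 contain no quality-of-life objective. In a table with one row per item, the wording would reveal the direction, leaving five rows under a misleading label.

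**Conclusion.** The concern holds. Followed literally, the rule misclassifies C6, GF5, GF1, GF3 and GF7 on raw answers and on oriented scores alike. That is the minimum error; on oriented scores the rule is reversed for all 19 items. The conclusion rests only on the item wording and common response scale in Appendix D and on the absence of any stated reversal or exemption.

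The effect on the reported proportions cannot be predicted, because the documents give no item response rates. The consequence is limited to one descriptive summary of a secondary endpoint. The FKSI-19 total, whose direction is fixed in 14.1.2, and the ORR, MTD, power and safety analyses are untouched. The text should be corrected before the quality-of-life tables are programmed, but the point does not bear on the trial's main conclusions.

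**What to change.** Add one or two sentences to 14.3.5:

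- The 3-or-4 cut-off applies to raw answers, as circled, on the 14 negatively worded items.
- For C6, GF5, GF1, GF3 and GF7 the item is reversed first, so that a raw 0 or 1 is flagged. Alternatively, these five items are left out of this summary.
- Each item stays in the instrument's own sub-domain.

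Reversal is preferable because it keeps every sub-domain populated; exclusion could leave the function and well-being summary partly or wholly empty. It would also help to say whether the pooled figure means any item flagged or a table with one row per item.

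The cost is the added text and a small change to the scoring code. Data collection does not change.

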14.3.6 Pharmacokinetic analyses

All PK concentration data (MK-6482, MK-6482 metabolites, abemaciclib, abemaciclib metabolites) will be listed in each arm and by dose cohort.

Blood samples for the determination of concentration of MK-6482, MK-6482 metabolite, abemaciclib, abemaciclib metabolites will be obtained before (pre-dose), 3 hours (\pm 15 minutes) post-dose at Cycle 1 Day 1 visit. The plasma concentrations of MK-6482, MK-6482 metabolites, abemaciclib, abemaciclib metabolites at each collection time will be summarized descriptively (n, arithmetic mean, standard deviation, minimum, median, maximum, and coefficient of variation) by arm and dose cohort. Figures displaying individual and mean plasma concentrations will be provided.

14.3.7 Pharmacodynamic analyses

Summary statistics (n, arithmetic mean, standard deviation, median, minimum, and maximum) for the observed data and percentage change from baseline will be presented for PD blood sample parameters by arm and dose cohort.

Blood samples for assessment of pharmacodynamic parameters such as EPO will be obtained as per schedule of events. Whole blood RNA and DNA samples will be used to determine genomic status of drug metabolizing enzymes and other hypoxia pathway components that may influence drug exposure and/or response to drug treatment.

The value, change from baseline, and percent change from baseline will be listed and summarized for each scheduled time-point during the study for each of the pharmacodynamic parameters.

14.3.8 Correlative Endpoints Analysis

The planned correlative analyses include (but are not limited to):

- molecular profiling using Oncopanel, whole exome sequencing and whole transcriptome sequencing.
- immunohistochemistry, immunofluorescence and other advanced imaging techniques to assess expression of oncogenic proteins on tumor cells
- candidate circulating immune markers before and during therapy

- circulating cell-free DNA (cfDNA) values during the course of therapy
- germline DNA from whole blood

Gene mutation frequencies and mean \pm SD of quantitative transcriptome will be summarized in overall population. It is anticipated that we will have tissue samples assayed in about 60% of participants (N=22) at baseline and in 40% (N=15) at progression.

Candidate circulating biomarkers and their changes from baseline will be summarized during the course of therapy. Normality will be assessed and appropriate transformation will be made at time of analysis. Paired T-test or Wilcoxon signed rank test will be conducted for any paired comparison between timepoints. Two-sample t-test or Wilcoxon rank sum test will be used to compare quantitative circulating biomarkers between responders and non-responders (by RECIST criteria) as exploratory analyses.

14.4 Safety monitoring

No formal stopping rule regarding the primary efficacy endpoints is planned. Adverse event reports are to be submitted within 28 days of each clinic visit. All relevant adverse events will be reviewed by the DSMC for up to 4 times each year. The DSMC will make recommendation to the study management team if it notes any concerns regarding patient safety or if further action needs to be taken based on the safety monitoring review results. Formal assessment of (targeted) adverse events will also be included in statistical analysis for secondary objectives as detailed in section 14.3.4.

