5.4 Definition of Dose-limiting Toxicity

For patients treated in arm 2, DLT will be defined as any abemaciclib or MK-6482 related toxicity resulting in discontinuation or dose reduction per the guidelines in the Section 6.2 to 6.87 within the first 28 days of treatment, for which there is no clear alternative explanation (i.e. disease related).

DLTs will be defined as any of the following events not clearly due to the underlying disease or extraneous causes:

- Any death
- Non-hematologic toxicity:
 - Grade 3 or higher
 - Hy's law cases
- Hematologic toxicity (for non-acute leukemia indications):
 - Grade 4 neutropenia for more than 7 days
 - Grade 3 or higher thrombocytopenia with clinically significant bleeding
 - Neutropenic fever

The DLT definition may exclude:

- Grade 3 nausea/vomiting or diarrhea for less than 72 hours with adequate antiemetic and other supportive care
- Grade 3 or higher electrolyte abnormality that lasts up to 72 hours, is not clinically complicated, and resolves spontaneously or responds to conventional medical interventions
- Grade 3 or higher amylase or lipase that is not associated with symptoms or clinical manifestations of pancreatitis

Patients within arm 2 who do not receive at least 80% of the intended abemaciclib plus MK-6482 doses during the first 28 days for reasons other than toxicity, will not be evaluable for DLTs and will be replaced. Once a tolerable dose combination has been determined in arm 2, patients will no longer be replaced in the study.

Dose escalation will proceed within each cohort according to **Table 4**. Dose-limiting toxicity (DLT) is defined above.

Table 4. Dose-escalation scheme

Number of Participants with DLT at a Given Dose Level	Escalation Decision Rule
0 out of 3	Enter 3 participants at the next dose level.
≥ 2	Dose escalation will be stopped. This dose level will be declared the maximally administered dose (highest dose administered). Three (3) additional participants will be entered at the next lowest dose level if only 3 participants were treated previously at that dose.

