1 out of 3	Enter at least 3 more participants at this dose level. 
 • If 0 of these 3 participants experience DLT, proceed to the next dose level. • If 1 or more of this group suffer DLT, then dose escalation is stopped, and this dose is declared the maximally administered dose. Three (3) additional participants will be entered at the next lowest dose level if only 3 participants were treated previously at that dose.
≤ 1 out of 6 at highest dose level below the maximally administered dose	This is generally the recommended phase 2 dose. At least 6 participants must be entered at the recommended phase 2 dose.

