14.2 Sample Size and Accrual

There is limited data regarding clinical activity of abemaciclib and MK-6482 in ccRCC. Activity of abemaciclib has been described in a phase 1 trial in solid tumors that did not involve ccRCC patients¹⁴. Response rates in advanced refractory breast cancer patients treated with abemaciclib single agent was 19.5%¹⁵.

MK-6482 is has been evaluated in a phase I/II trial involving patients with refractory ccRCC. Preliminary data showed that among 55 patients treated at the MTD, objective response rate was 22%. Toxicities involved mainly anemia, hypoxia and edema. Drug discontinuations due to adverse events were less than 10%.

Therefore, in arm 1, planned sample size is 11 patients, allowing a 0.80 probability to observe 2 or more responses if the true ORR is 25% or higher.

Arm 2 will evaluate two dose levels and follow a standard 3+3 dose escalation scheme. Once the MTD is determined and 6 patients have been treated at the MTD, 14 additional patients will be enrolled for a total of 20 patients treated at the MTD. As ORR is 20-25% for ccRCC patients treated with MK-6482 single-agent, we target an ORR of 50% for the combination of abemaciclib plus MK-6482. With a planned sample size of 20 patients treated at the MTD, there is 94% power to distinguish an ORR of 50% from an ORR of 20% under one-stage design (one-sided alpha=0.09). The combination is considered effective if 7 or more responses are observed out of 20.

The total enrollment will be up to 37 patients (11 in arm 1 and 23~26 patients in arm 2). The accrual is expected to be 3-4 patients per month for a duration of 12 months to complete enrollment.

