15.5 Study Medical Monitoring Requirements

This clinical research study will be monitored both internally by the PI and externally by the IRB. In terms of internal review, the PI will continuously monitor and tabulate AEs. Appropriate reporting to the IRB will be made. The PI of this study will also continuously monitor the conduct, data, and safety of this study to ensure that:

- Interim analyses occur as scheduled,
- Stopping rules for toxicity and/or response are met,
- Risk/benefit ratio is not altered to the detriment of the subjects,
- Appropriate internal monitoring of AEs and outcomes is done,
- Over-accrual does not occur,
- Under-accrual is addressed with appropriate amendments or actions, and
- Data are being appropriately collected in a reasonably timely manner.

Routine monitoring will be carried out via a periodic team conference among investigators during which toxicity data, including all SAEs, will be reviewed and other issues relevant to the study such as interim assessment of accrual, outcome, and compliance with study guidelines, will be discussed. Monitoring will be carried out on an ongoing basis. The severity, relatedness, and whether or not the event is expected will be reviewed.

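### No numeric toxicity limit covers the 14 expansion patients at the MTD: the only DLT rule ends at 6 patients, and the plan does not say what later DLTs do

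*Combined protocol and SAP*

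**What the plan says.** Section 14.3.3 gives the only numeric dose rule: "MTD is defined as the highest dose studied at which no more than 1 of 6 subjects has experienced a DLT in cycle 1". Sections 5.1 and 14.1.1 repeat it. Table 4 in section 5.4 supplies the escalation steps. Two or more DLTs stop escalation. After 1 of 3, three more patients enter, and "If 1 or more of this group suffer DLT, then dose escalation is stopped, and this dose is declared the maximally administered dose". So 2 of 6 rejects a dose and 1 of 6 clears it. Section 14.3.3 adds that after the first three to six patients "a safety evaluation will be done by the overall PI before any further patients are enrolled".

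Section 14.2 then expands: "14 additional patients will be enrolled for a total of 20 patients treated at the MTD". Section 5.4 defines a DLT for patients treated in arm 2, so expansion patients can have DLTs, but no section uses them in a cohort decision. Replacement of patients not evaluable for DLT ends at the same point: "Once a tolerable dose combination has been determined in arm 2, patients will no longer be replaced in the study".

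On monitoring, 14.4 rules out a formal stopping rule for the primary efficacy endpoints and provides DSMC review up to four times a year: "The DSMC will make recommendation to the study management team if it notes any concerns regarding patient safety". It also states: "Adverse event reports are to be submitted within 28 days of each clinic visit". Section 15.5 lists among the matters the PI is to ensure: "Stopping rules for toxicity and/or response are met". No toxicity stopping rule is written anywhere beyond the 3+3.

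**The concern.** The MTD is a co-primary objective of arm 2, and ORR is assessed at that dose. Fourteen of the 20 patients at the MTD (70%) are treated after the last numeric toxicity criterion has been applied. Six patients say little about a DLT rate: the exact 95% confidence interval for 1 of 6 runs from 0.4% to 64%.

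The consequence is uneven. In escalation, 2 of 6 (33%) rejects a dose. In the full MTD cohort, 7 of 20 (35%) has no stated consequence. Whether to go on enrolling, and what to say about the dose at the end, would be decided after the data are seen and without an agreed limit. Section 15.5 adds to this by pointing to toxicity stopping rules that a reader cannot find.

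**Working it through.** **1. The plan's own figures.** The documents give no operating characteristics for toxicity. Those for response in the same 20 patients reproduce by exact binomial: P(X ≥ 7 | 20, 0.20) = 0.087 (stated 0.09) and P(X ≥ 7 | 20, 0.50) = 0.942 (stated 94%). That 7 of 20 is also the first count above one third is a coincidence; below it refers to DLTs.

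**2. Inputs.** Clearance at no more than 1 DLT in 6 (14.3.3); 14 further patients, 20 in total (14.2); accrual 3–4 per month (14.2); 28-day DLT window (5.4). The DLT rate p of the combination is not in the documents, so I assume 10% to 50%; 33% means one third.

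**3. Clearance.** With q = 1 − p, a dose clears with 0 of 3 then at most 1 of 3, or 1 of 3 then 0 of 3. This equals q⁶ + 6pq⁵. At p = 0.40: 0.0467 + 0.1866 = 0.233.

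**4. Seven or more DLTs in 20.** The joint probability is
P(0 of 6) × P(≥ 7 of 14) + P(1 of 6) × P(≥ 6 of 14).
At p = 0.40: 0.0467 × 0.3075 + 0.1866 × 0.5141 = 0.110. Dividing by 0.233 gives 0.473 given clearance.

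| Assumed DLT rate | Cleared | ≥ 7 of 20, given cleared | Cleared and ≥ 7 of 20 | Expected DLTs in the 14 |
|---|---|---|---|---|
| 10% | 0.886 | 0.001 | 0.001 | 1.4 |
| 15% | 0.776 | 0.007 | 0.005 | 2.1 |
| 20% | 0.655 | 0.031 | 0.020 | 2.8 |
| 33% | 0.351 | 0.270 | 0.095 | 4.7 |
| 40% | 0.233 | 0.473 | 0.110 | 5.6 |
| 50% | 0.109 | 0.762 | 0.083 | 7.0 |

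The joint probability peaks at 0.11, near 40%. These figures are for a dose that is tested. Level 2 is tested only if level 1 passes. At an assumed 20% rate at level 1 that has probability q³ + 3pq⁵ = 0.709, so the peak for level 2 is 0.709 × 0.110 = 0.08.

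**5. A one-third pause rule.** Start from 0 or 1 DLT in 6, given clearance. Add three patients at a time and pause at 3 of 9, 4 of 12 or 5 of 15. At p = 0.40 the starting weights are 0.2 and 0.8. The first look gives 0.2 × 0.064 + 0.8 × 0.352 = 0.294; later first pauses add 0.159 and 0.102, in total 0.555.

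| Assumed DLT rate | 10% | 15% | 20% | 33% | 40% | 50% |
|---|---|---|---|---|---|---|
| P(pause), given cleared | 0.02 | 0.05 | 0.12 | 0.39 | 0.56 | 0.77 |

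**6. Timing.** Fourteen patients accrue in 14/4 = 3.5 to 14/3 = 4.7 months. At no more than four DSMC reviews a year, one or two fall in that period. During a 28-day window (28/30.4 months) 2.8 to 3.7, so about 3–4, more patients may enrol.

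**The case against.** The strongest reply is that these patients are closely watched. Section 6 sets dose changes for each patient. SAEs go to the sponsor within 24 hours (7.3.1), and Table 14 sends grade 4 events (unless exempted as expected) and unexpected related grade 2–3 events within 10 calendar days. Investigator conferences review toxicity (15.5), and site teleconferences are roughly monthly (Appendix C, 4.1). Section 13.1.3 lists DLT information among the items the DSMC may receive. Section 5.10 ties the PI's power to stop to the incidence and severity of adverse events, which is a cohort criterion. All of this stands: a reader who inferred that the expansion is unmonitored would be wrong. What is missing is a number. One route is also slow: a non-serious, expected grade 3 DLT falls outside both the 24-hour SAE rule and the 10-day rule.

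A reader might also infer that later DLTs cannot change the MTD. The documents do not say so. They define the MTD on 6 subjects and are silent on later data; they neither forbid a revision nor describe one.

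The two-or-more row of Table 4 has no denominator and might be read as covering the expansion. It sits in an escalation scheme. Over 20 patients it would trip with probability 1 − 0.9²⁰ − 20 × 0.1 × 0.9¹⁹ = 0.61 at a 10% rate, so that reading is implausible.

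Finally, the true rate may be low. Section 2.3.1 reports no DLT for MK-6482 at 20–160 mg, and abemaciclib is capped at 150 mg bid here against 200 mg alone. That is why the range starts at 10%. It does not settle the matter: grade 3 diarrhea was 20% and fatigue 13% with abemaciclib alone (7.1.1), although not restricted to cycle 1.

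**Conclusion.** The concern holds as a missing numeric limit, not as missing oversight. The one numeric cohort rule ends at 6 patients. No text states what cycle 1 DLTs among the 14 expansion patients do to enrolment or to the MTD conclusion, and 15.5 points to toxicity stopping rules that are not written.

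The size is modest. Before the trial starts, the chance that a tested dose is cleared and then shows 7 or more DLTs in 20 is at most 0.11 at any DLT rate, and 0.02 or less at 20% or below. The conditional figures of 0.27 at 33% and 0.47 at 40% apply only once a dose has been cleared, and should not be quoted as the overall risk. All of this rests on assumed DLT rates and on independence between patients. The one-third limit is a choice that carries forward the 2-of-6 rejection proportion; the documents state no target DLT rate. The change should be made because it costs little and gives most of the MTD cohort an agreed limit.

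**What to change.** Add to 14.4:

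> Cycle 1 DLTs will be counted in all DLT-evaluable patients treated at the MTD, and sites will report them to the Overall PI within 24 hours. Enrolment pauses for PI and DSMC review if DLTs reach 3 of the first 9, 4 of 12 or 5 of 15 (one third, the proportion that rejects a dose in the 3+3).

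Point 15.5 to this rule. Report the DLT rate with an exact confidence interval in all evaluable patients at the MTD. If it is one third or more (7 or more of 20), state this beside the MTD conclusion and have the PI and DSMC review the recommended dose. Do not remove the MTD label automatically: 5.1, 14.1.1 and 14.3.3 define it on 6 subjects, and the ORR endpoint would lose its defined population.

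The rule uses cycle 1 data already collected; the only new burden is 24-hour DLT reporting. The price is an occasional pause at a tolerable dose (step 5 of the working). The 3–4 patients who may enrol before a limit is recognised limit the protection. A pause that becomes a stop leaves fewer than 20 patients for the ORR test.
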